#### **LGG Cohort**

With respect to the LGG cohort the secondary objectives related to efficacy in this study are to compare the two treatment groups with respect to the overall response rate (ORR) by investigator assessment, duration of response (DOR), time to response (TTR), clinical benefit rate (CBR), and progression-free survival (PFS) by both investigator assessment and central independent assessment as well as overall survival (OS), safety, and patient reported outcome (PRO).

All secondary efficacy analyses will be performed based on the FAS and will be repeated for the Evaluable set. All secondary endpoints will be listed and summarized separately for each cohort by treatment group.

For the LGG cohort, a hierarchical approach will be taken to control for the overall type-I error rate for testing of multiple endpoints: PFS will be formally tested only if the primary endpoint ORR is statistically significant and then OS will be formally tested if PFS is also significant. No other multiplicity adjustments are planned for secondary endpoints testing.

#### **ORR** by investigator assessment (HGG Cohort)

For the HGG cohort, the evaluation of ORR will be repeated by investigator assessment as per RANO criteria. ORR will be summarized using descriptive statistics (N, %) along with 2-sided exact 95% confidence intervals (CIs) (Clopper and Pearson 1934). 80% confidence intervals will also be provided for the HGG cohort.

#### **ORR** by investigator assessment (LGG Cohort)

For the LGG Cohort the evaluation of ORR will be repeated by investigator assessment assessment as per RANO criteria.

The Cochrane-Mantel-Haenszel chi-square test will be used to compare ORR between the two treatment groups, at the one-sided 2.5% level of significance.

#### **Duration of response**

Among patients with a confirmed response (PR or CR) per RANO, duration of response (DOR) is defined as the time from first documented response (PR or CR) to the date of first documented disease progression or death due to any cause. DOR will be listed by patient and may be

described using Kaplan-Meier curves and relevant statistics if appropriate. Only the subset of patients who show a confirmed complete or partial tumor response will be included. Censoring rules for DOR will be outlined in detail in the SAP. DOR will be analyzed as per investigator assessment and as per central independent assessment, separately.

#### **Progression free survival**

Progression-free survival (PFS) is defined as the time from the date of first dose of study treatment (for HGG cohort) or date of randomization (for LGG cohort) to the date of first documented disease progression per RANO criteria or death due to any cause.

A patient who has not progressed or died or has received any further anticancer therapy at the analysis cut-off date, PFS will be censored at the time of the last adequate tumor evaluation before the cut-off date or before the start of the new anticancer therapy date, whichever is earlier. By default, if disease progression or death is documented after one single missing tumor evaluation, the actual event date of disease progression/death will be used for the PFS event date. If disease progression or death is documented after two or more missing tumor evaluations, the PFS time of these patients will be censored at the date of the last adequate tumor evaluation without PD. Censoring rules for PFS will be described in detail in the SAP.

PFS assessed by the investigators and the central independent reviewers will be described using Kaplan-Meier methods and appropriate summary statistics.

For the LGG cohort the hazard ratio for PFS will be calculated, along with its 95% confidence interval, using a Cox model. A log-rank test at the one-sided 2.5% level of significance will be used to compare the two treatment groups.

PFS estimates (and 95% CIs) for both cohorts will be provided for key timepoints (i.e. 12, 24, 36 months).

#### Time to response (TTR)

Time to response (CR or PR) is the time from start date of study treatment (for HGG cohort) or date of randomization (for LGG cohort) to first documented response of CR or PR (which must be confirmed subsequently) according to RANO criteria. All patients in the FAS will be included in the time to response calculations. Patients without a confirmed CR or PR will be censored at the study-maximum follow-up time (i.e., LPLV-FPFV) for patients with a PFS event (i.e., disease progression or death due to any cause), or at the date of the last adequate tumor assessment for patients without a PFS event. TTR will be listed and summarized by treatment group.

The distribution of time to response will be estimated using the Kaplan-Meier method and the median time to response will be presented along with 95% confidence interval only if a sufficient number of responses is observed. A responders-only analysis will also be performed in this case.

TTR will be analyzed using investigator and independent reviewer assessments separately.

Clinical benefit rate (CBR) is defined as the proportion of patients with a best overall response of CR or PR, or an overall lesion response of SD which lasts for a minimum time duration of at least 24 weeks. A patient will be considered to have SD for 24 weeks or longer if a SD response is recorded at 23 weeks or later (i.e  $\geq$ = 161 days) from randomization, allowing for the  $\pm$ 1 week visit window for tumor assessments.

For the HGG cohort, CBR will be summarized using descriptive statistics (N, %) along with 2-sided exact 95% confidence intervals (CIs) (Clopper and Pearson 1934).

For the LGG Cohort, CBR will be summarized by treatment group along with 2-sided exact 95% confidence intervals (CIs). Cochrane-Mantel-Haenszel chi-square test will be used to compare CBR between the two treatment groups, at the one-sided 2.5% level of significance.

#### Overall survival

Overall survival (OS) is defined as the time from the date of first dose of study treatment (for HGG cohort) or date of randomization (for LGG cohort) to the date of death due to any cause. OS time for patients who are alive at the end of the study or are lost to follow-up will be censored at the date of last contact.

OS will be described using Kaplan-Meier methods and appropriate summary statistics.

For the LGG cohort, the hazard ratio for OS will be calculated, along with its 95% confidence interval, using a Cox model. A log-rank test at the one-sided 2.5% level of significance will be used to compare the two treatment groups.

In addition, 2-year OS estimate with corresponding 95% CIs will be provided by treatment groups.

#### 10.5.1 Safety objectives

Safety will be assessed separately for the HGG and LGG cohorts. For the LGG cohort the data will be analyzed by treatment arm.

#### 10.5.1.1 Analysis set and grouping for the analyses

For all safety analyses in both cohorts, the safety set will be used. All listings and tables will be presented by all patients.

The overall observation period will be divided into three mutually exclusive segments:

- 1. Pre-treatment period: from day of patient's informed consent to the day before first dose of study medication
- 2. On-treatment period: from day of first dose of study medication to 30 days after last dose of study medication
- 3. Post-treatment period: starting at day 31 after last dose of study medication.

The safety summary tables will include only data collected during the on-treatment period. However, all safety data will be listed with data collected during the pre-treatment and post-treatment period flagged.

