LGG patients receiving carboplatin with vincristine treatment will follow the regimen in Section 6.1.2 in conjunction with institutional practice. Duration of treatment should continue for the prescribed number of cycles as tolerated, or until unacceptable toxicity, start of a new anti-neoplastic therapy, discontinuation at the discretion of the investigator or patient/legal guardian, lost to follow-up, death, study termination by the sponsor, or until disease progression. See Section 6.3.1.16 for dose modifications and management guidelines or carboplatin with vincristine. Patients randomized to the carboplatin with vincristine treatment arm will only be allowed to cross over to receive dabrafenib in combination with trametinib after centrally confirmed RANO-defined disease progression. Crossover will be allowed during the treatment period or the post-treatment period.

LGG patients on dabrafenib with trametinib treatment may continue to receive the assigned study treatment until disease progression by RANO criteria or loss of clinical benefit as determined by the investigator, unacceptable toxicity, start of a new anti-neoplastic therapy, discontinuation at the discretion of the investigator or patient/legal guardian, lost to follow-up, death, or study termination by the sponsor.

LGG patients receiving dabrafenib with trametinib who have disease progression by RANO criteria may continue study treatment if the investigator determines that patient has clear evidence of clinical benefit from study treatment, continuing study treatment may be in the best interest for the patient, and the patient/legal guardian is willing to continue on study treatment and sign the Informed Consent for treatment beyond progression. The decision to continue study treatment after PD must be documented in the patient records and eCRF after every tumor

evaluation. In this case, the patient will continue assessments as defined in Section 7. An End

of Treatment visit will be performed when patients permanently discontinue study treatment.

Patients who discontinue dabrafenib with trametinib treatment or complete carboplatin with vincristine treatment without disease progression by RANO criteria will continue tumor assessment as part of the post treatment follow-up outlined in Section 7 until central independently confirmed disease progression by RANO criteria or death irrespective of start of new anti-neoplastic therapy.

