#### 4.1.2.2 Crossover and Continuation of Treatment (LGG Cohort)

For the LGG cohort, patients randomized to the carboplatin with vincristine treatment arm will be allowed to crossover to receive dabrafenib in combination with trametinib treatment after centrally confirmed and RANO-defined disease progression. Patients who cross over are expected to continue to undergo protocol specified evaluations according to Table 7-2, including efficacy and safety assessments.

LGG patients who crossover to receive dabrafenib in combination with trametinib must continue to meet the inclusion criteria for cardiac function, be willing to follow all contraception guidance, and cannot meet the exclusion criteria for allergy to dabrafenib, trametinib, or their excipients. Measurable disease is not mandatory but a new baseline tumor evaluation must be established within 28 days of starting dabrafenib in combination with trametinib crossover treatment. Day 1 of crossover therapy must occur within 90 days from the date of the first centrally confirmed progression. After the final PFS analysis and assuming significant favorable ORR and favorable PFS for the experimental therapy, patients randomized to carboplatin plus vincristine arm with persistent stable disease and deemed suitable for further systemic therapy for their disease may be allowed to crossover to receive dabrafenib in combination with trametinib.

PRO, taste questionnaires and pharmacokinetic samples will not be obtained on those patients who cross over to receive dabrafenib plus trametinib therapy.

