#### 6 Treatment

## 6.1 Study treatment

In this study, the term "study treatment or drug" refers to Novartis study drug dabrafenib (DRB436) with trametinib (TMT212) or carboplatin and vincristine.

Refer to Section 6.1.1.1 for dabrafenib (DRB436) and trametinib (TMT212) dosing instructions. Refer to Section 6.1.2 for carboplatin and vincristine dosing instructions.

All dosages prescribed and dispensed to the patient and all dose changes during the study must be recorded on the Dosage Administration Record eCRF.

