### 10.1.2 Safety set

The Safety Set for both HGG and LGG cohort include all patients who received at least one dose of study treatment.

For the LGG cohort, patients will be analyzed according to the study treatment received, where treatment received is defined as the randomized treatment if the patient took at least one dose of that treatment or the first treatment received if the randomized treatment was never received.

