#### 10.5.1.2 Adverse events (AEs)

Summary tables for adverse events (AEs) will include only AEs that started or worsened during the on-treatment period, the treatment-emergent AEs.

The incidence of treatment-emergent AEs (new or worsening from baseline) will be summarized by system organ class and/ or preferred term, severity (based on CTCAE grades), type of AE, and relation to study treatment.

Serious adverse events (SAE), non-serious adverse events and adverse events of special interest (AESI) during the on-treatment period will be tabulated.

All deaths (on-treatment and post-treatment) will be summarized.

All AEs, deaths and serious adverse events (including those from the pre and post-treatment periods) will be listed and those collected during the pre-treatment and post-treatment period will be flagged. A listing of all grouping levels down to the MedDRA preferred terms used to define each AESI will be generated.

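### The LGG on-treatment window is not limited to the randomised regimen, so events starting on crossover dabrafenib/trametinib can be tabulated as chemotherapy events

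*Protocol*

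**What the plan says.** Section 10.5.1.1 of the protocol divides follow-up into three segments. The middle one is "On-treatment period: from day of first dose of study medication to 30 days after last dose of study medication", and "The safety summary tables will include only data collected during the on-treatment period". Section 10.5.1.2 applies this to adverse events: "Summary tables for adverse events (AEs) will include only AEs that started or worsened during the on-treatment period". Section 10.5.1.3 builds laboratory shift tables from baseline to the worst on-treatment value.

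On grouping, section 10.5.1 states: "For the LGG cohort the data will be analyzed by treatment arm". Section 10.1.2 nominally groups LGG patients by treatment received, but then "treatment received is defined as the randomized treatment if the patient took at least one dose of that treatment". Section 10.5.1.1 also speaks of presenting tables by all patients, which sits awkwardly beside the by-arm rule. The by-arm sentence is taken here as governing the LGG cohort.

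Section 6.1 says that the term study treatment or drug "refers to Novartis study drug dabrafenib (DRB436) with trametinib (TMT212) or carboplatin and vincristine". The glossary is equally broad and covers drugs in any study arm. Under section 4.1.2.2, after centrally confirmed progression, "patients randomized to the carboplatin with vincristine treatment arm will be allowed to crossover to receive dabrafenib in combination with trametinib treatment". Section 4.1 adds: "Crossover will be allowed during the treatment period or the post-treatment period".

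**The concern.** Safety and tolerability against chemotherapy is a stated secondary objective of the LGG cohort. A control patient who crosses over receives the experimental drugs on study, with continuous adverse event collection under Table 7-2. If that patient stays in the chemotherapy column and the window stays open until 30 days after the last crossover dose, toxicity that begins on dabrafenib/trametinib is reported as control-arm toxicity. Incidence proportions and worst-value shifts in the control column can then only rise, and they rise most for the events typical of the experimental drugs. The contrast narrows and the experimental arm looks better than it should. More patients will have crossed over by the final analysis, so the distortion would grow with follow-up.

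**Working it through.** The protocol states no figure to reproduce. The check is to apply its definitions in order to one patient randomised to chemotherapy who takes at least one dose and later crosses over.

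1. **Column.** Sections 10.1.2 and 10.5.1 place the patient under carboplatin with vincristine, and crossover does not change that.
2. **Is crossover treatment study medication?** Study medication is not defined as a separate term. The related definitions (glossary, 6.1) cover both regimens. Section 2.6 describes patients crossing over as part of their study treatment, and Table 7-2 lists both drugs under study drug administration.
3. **End of window.** On those definitions the last dose is the last crossover dose. Section 7.1.6 applies the 30-day follow-up to the crossover schedule as well as to the other two.
4. **What is tabulated.** Sections 10.5.1.1 to 10.5.1.3 include everything in the window. Nothing in 10.5.1 cuts it at crossover, and nothing gives crossover its own column or safety baseline.

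So an event that first appears on crossover treatment is treatment-emergent in the chemotherapy column.

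**Illustration of size.** Inputs:
- Controls: 102 randomised 2:1, so 102/3 = 34 (sections 4.1 and 10.8.2).
- p, incidence on the paediatric combination: pyrexia 58%, rash 67% (section 1.2.3.1, 12 patients, three of them on half-dose dabrafenib).
- q, incidence on chemotherapy, and c, number crossing over: assumed, because the protocol gives neither.

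Simple upper bound on the points added: (c/34) × p. Allowing for patients who already had the event on chemotherapy, and assuming independence, the tabulated control incidence is q + (c/34) × (1 − q) × p. For c = 10, q = 10% and pyrexia: 0.10 + (10/34) × 0.90 × 0.58 = 0.254.

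| c of 34 | Upper bound added, pyrexia (points) | Tabulated pyrexia, q = 10% | Arm difference (58% minus tabulated; 48 points if cut at crossover) | Tabulated rash, q = 10% |
|---|---|---|---|---|
| 3 | 5.1 | 14.6% | 43.4 | 15.3% |
| 7 | 11.9 | 20.7% | 37.3 | 22.4% |
| 10 | 17.1 | 25.4% | 32.6 | 27.7% |
| 17 | 29.0 | 36.1% | 21.9 | 40.2% |

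With q between 5% and 20% and c between 3 and 17, tabulated pyrexia runs from 9.9% to 43.2%.

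**The case against.** The strongest reply is that the protocol can be read regimen by regimen.

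- Section 4.1 allows crossover in the post-treatment period, while 10.5.1.1 starts its post-treatment segment on day 31 after the last dose. If the last dose always meant the last crossover dose, nobody could be in that segment before crossing over.
- Table 7-2 gives crossover its own pre-treatment column, Week 1, end-of-treatment visit and post-treatment period. Table 7-3 gives chemotherapy its own end-of-treatment visit and follow-up.
- Section 7.1.6 names all three schedules, so it fits a per-regimen reading equally well.
- Section 10.4.4 leaves analyses of crossover data to the SAP, in words not confined to efficacy.
- Adverse events are also summarised by relation to study treatment, and section 8.2.2 asks for the relationship of each serious event to each specific treatment.

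Much of this stands. It shows that the literal reading is not the only one and that the protocol does not use its terms consistently. It does not settle the point. The visit tables govern visits, and no safety section carries their phases into the analysis window. The sentence in 10.4.4 sits among supportive analyses of the primary efficacy objective, while the safety window and grouping are fixed elsewhere without restriction. Causality coding does not move an event out of the chemotherapy column.

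Two stronger readings should be resisted. A reader might infer that the window expressly runs to the last dose of any study drug; the text does not say any, and that breadth comes from definitions of neighbouring terms. A reader might also infer that an untreated gap between chemotherapy and crossover is deliberately counted as on-treatment; section 4.1 places some crossovers in the post-treatment period, so the documents do not support stating that as the plan.

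**Conclusion.** The point holds as a badly fixed rule, not as proof of how the tables will be produced. The protocol fixes the control column for crossover patients and fixes a window that is not limited to the randomised regimen. Read with its broad definition of study treatment, this puts toxicity of crossover dabrafenib/trametinib in the chemotherapy column and biases the LGG safety comparison towards the experimental arm. The same reading fits poorly with section 4.1 and with Tables 7-2 and 7-3, which is a further reason to settle it in the text.

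The direction is clear on that reading; the size is not known. Crossover fraction times event rate is only an upper bound, the event rates come from 12 patients, and the crossover number and the chemotherapy incidence are assumptions. The effect is probably small at the primary analysis, which requires 32 weeks of treatment or earlier discontinuation, because crossover then needs centrally confirmed progression. It is likely larger at the final analysis, at least two years after the last patient's first treatment. Section 4.1.2.2 also foresees possible crossover of patients with stable disease after the final PFS analysis.

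**What to change.** In section 10.5.1.1, define the LGG control arm's on-treatment period for safety tables as running from the first chemotherapy dose to the earlier of 30 days after the last chemotherapy dose and the day before the first crossover dose. Summarise the crossover period, from the first crossover dose to 30 days after the last, in a separate column. Use a pre-crossover baseline where Table 7-2 collects one; its pre-treatment column includes vital signs, ECG and echocardiogram. This also brings the safety window into line with section 4.1, because any gap beyond 30 days after chemotherapy falls outside the on-treatment period.

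The cost is one sentence and one extra table column. The crossover data are already collected under Table 7-2, and the change concerns analysis only.

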#### 10.5.1.2 Adverse events (AEs)

Summary tables for adverse events (AEs) will include only AEs that started or worsened during the on-treatment period, the treatment-emergent AEs.

The incidence of treatment-emergent AEs (new or worsening from baseline) will be summarized by system organ class and/ or preferred term, severity (based on CTCAE grades), type of AE, and relation to study treatment.

Serious adverse events (SAE), non-serious adverse events and adverse events of special interest (AESI) during the on-treatment period will be tabulated.

All deaths (on-treatment and post-treatment) will be summarized.

All AEs, deaths and serious adverse events (including those from the pre and post-treatment periods) will be listed and those collected during the pre-treatment and post-treatment period will be flagged. A listing of all grouping levels down to the MedDRA preferred terms used to define each AESI will be generated.

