The LGG cohort is a randomized comparison of dabrafenib with trametinib versus chemotherapy in the treatment of chemotherapy naïve patients with *BRAF* V600 mutant LGG whose tumor is unresectable and who require treatment. Eligible patients will have locally determined *BRAF* V600 mutant LGG with both local and centrally confirmed measurable disease. Approximately 102 patients will be randomized in a 2:1 ratio to either dabrafenib with trametinib or carboplatin with vincristine chemotherapy. Treatment with carboplatin plus vincristine will continue until completion of the prescribed chemotherapy regimen. Treatment with dabrafenib plus trametinib will continue until disease progression or patients are no longer receiving clinical benefit in the opinion of the investigator, death, or unacceptable toxicity. After discontinuation of the study treatment, patients will remain on the study for follow-up assessments and collection of information on subsequent anti-cancer treatments and survival.

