# 6.1.2 Carboplatin and Vincristine Dosing Regimen

Carboplatin and vincristine will be supplied locally as commercially available and labelled accordingly to comply with legal requirements of each country. Carboplatin and vincristine will be administered as one course of induction (10 weeks of chemotherapy with 2 weeks of rest), followed by 8 cycles of maintenance chemotherapy. Each maintenance cycle is 6 weeks. Maintenance cycles are only given following sufficient recovery of hematologic parameters.

Chemotherapy administration should follow the guidelines below and as per local product labels or SmPC. Please consult local product labels and institutional standards for duration of infusion and flush requirements when administering carboplatin and vincristine.

Local safety laboratory testing to confirm hematologic parameters may be conducted per institutional practice during induction and maintenance phases of chemotherapy prior to dosing when central labs are not scheduled per protocol or when central lab results will not be available prior to dosing. Results will be collected in the eCRF.

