# 10 Statistical methods and data analysis

The data from all participating centers in this protocol will be combined.

The data for the HGG and LGG cohorts will be analyzed independently with timing of analyses based on specific independent criteria for each cohort outlined in this protocol.

Note that there may be a need to support the initial submission of an indication based on the primary analysis data with safety and PK interim data from both cohorts. Thus the initial planning of the primary analysis for a specific cohort should anticipate that a safety interim or update analysis of the other cohort may also be required.

The primary endpoint for the HGG cohort will be analyzed at the time of the interim analysis and the study may be stopped for futility according to the criteria described in the Interim Analysis Section (Section 10.7). If the HGG cohort is not stopped at interim analysis then the

primary analysis of the HGG cohort will be conducted at the time when all treated patients have either completed at least 32 weeks of treatment or have discontinued earlier. These data will be summarized in the primary Clinical Study Report (CSR). The final analysis of the HGG cohort will be conducted at the end of the study as specified in Section 4.3. All available data from all HGG cohort patients up to the end of study cutoff date will be analyzed.

The primary analysis for the LGG cohort will be conducted when all treated patients have either completed at least 32 weeks of treatment or have discontinued earlier. These data will be summarized in the primary CSR.

The final analysis of LGG cohort will be conducted at the end of the study as specified in Section 4.3. All available data from all LGG cohort patients up to the end of study cutoff date will be analyzed.

All data will be summarized by treatment group and included in listings.

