#### 10.7.2 **LGG Cohort**

No formal interim analysis is planned for the LGG cohort. The primary analysis will be performed after all patients have completed Week 32 or discontinued prior to Week 32. A final analysis will be performed after all patients have been on the study for at least two years (or otherwise discontinued from the study). Formal testing of the primary endpoint with full alpha will be performed at the primary analysis.

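### At the LGG final analysis, by-arm adverse event incidence compares a chemotherapy window of about 62 weeks with open-ended D+T exposure, so events that keep accruing can look more frequent on D+T from longer time at risk alone

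*Protocol*

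**What the plan says.** The protocol summary and Table 3-1 make the safety of D+T versus carboplatin with vincristine a secondary objective of the LGG cohort. Section 10.5.1 adds: "For the LGG cohort the data will be analyzed by treatment arm". Section 10.5.1.2 sets the measure: "The incidence of treatment-emergent AEs (new or worsening from baseline) will be summarized by system organ class and/ or preferred term". Section 10.5.1.1 defines the period that counts: "On-treatment period: from day of first dose of study medication to 30 days after last dose of study medication". The summary tables hold on-treatment data only; later events appear in listings.

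The two treatments differ in planned length. Section 2.2 says of the control arm: "Treatment with carboplatin plus vincristine will continue until completion of the prescribed chemotherapy regimen". Of the experimental arm it says: "Treatment with dabrafenib plus trametinib will continue until disease progression", or until loss of clinical benefit, death or unacceptable toxicity. Section 4.1.2.1 also permits D+T beyond progression. Table 7-3 places the last carboplatin block in weeks 55 to 58. Delays are possible, since section 6.1.2 says: "Maintenance cycles are only given following sufficient recovery of hematologic parameters".

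Section 10.7.2 sets the timing of the last look: "A final analysis will be performed after all patients have been on the study for at least two years". Section 10 says of it: "All available data from all LGG cohort patients up to the end of study cutoff date will be analyzed". Section 10.3 summarises duration of exposure for both arms, but separately from the event tables.

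**The concern.** A percentage of patients with at least one event depends on the event rate and on how long patients are observed. If the windows differ systematically between arms, the two percentages mix both. For events confined to the first months this hardly matters. For events that continue to arise on treatment, the arm with the longer window shows more of them even when the rate per unit time is the same.

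Section 8.1.3 lists events of special interest that could behave this way, such as new primary or secondary malignancy. For long-term treatment of children, a reader of the final report will want to know whether such an event is more frequent per unit time on D+T or was simply observed for longer. By-arm incidence alone cannot answer that. The bias runs against the experimental arm.

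**Working it through.** **1. Chemotherapy window.** Induction takes 12 weeks (6.1.2). Seven six-week maintenance cycles precede the eighth, so cycle 8 starts in week 12 + 7 × 6 + 1 = 55. Carboplatin is given in weeks 1 to 4 of a cycle (6.1.2.2), so the last dose falls in week 58, as Table 7-3 shows. Adding 30 days: 58 + 30/7 = 62.3 weeks, or 1.19 years. A patient still on D+T at the final analysis has at least 104 weeks at risk, and 104/62.3 = 1.67.

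**2. Inputs for the illustration.** The protocol gives no event hazards and no discontinuation rates, so these are assumptions.
- Accrual: the amendment history gives 14 LGG patients randomised by 28-Feb-2019 and 44 by 26-Nov-2019, that is 30 in 271 days. Scaled to 102 patients: 102 × 271/30 = 921 days (2.52 years), taken as uniform.
- Cuts: 32 weeks (primary) and 2 years (final) after the last patient starts.
- D+T stopping: exponential, with median 52 weeks (assumed), 85 weeks or 104 weeks. The 85 comes from 1.2.3.1 (12 patients, 4 off treatment, median 41 weeks on treatment): ln 2 × 12 × 41/4 = 85, using the median as a mean. The 104 is the 24-month median on dabrafenib monotherapy in 1.2.1.2.1.
- The same constant hazard λ in both arms. The chemotherapy window closes at last chemotherapy dose + 30 days.

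**3. Formulas.** Let d = 30 days = 0.082 years, and let μ be the D+T stopping hazard (ln 2 divided by the median in years). Let F be follow-up, uniform from 2 to 4.52 years at the final cut.
- Chemotherapy: 1 − exp(−λ × 1.19).
- D+T: 1 − exp(−λd) × (μ + λA)/(λ + μ), where A is the average of exp(−(λ + μ)(F − d)) over F.

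**4. Numbers at λ = 0.3 per year, final cut.** Chemotherapy: 1 − exp(−0.358) = 30.1%. D+T at median 104 weeks: μ = 0.348, A = 0.142, exp(−λd) = 0.976, giving 1 − 0.976 × (0.348 + 0.0427)/0.648 = 41.2%.

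| Hazard, equal in both arms | D+T, median 52 / 85 / 104 weeks | Chemotherapy |
|---|---|---|
| 0.3 per year, final | 30% / 38% / 41% | 30% |
| 0.1 per year, final | 12% / 16% / 17% | 11% |
| 0.05 per year, final | 6% / 8% / 9% | 6% |
| Halving every 52 weeks, final | 27% / 31% / 33% | 30% |
| Halving every 26 weeks, final | 26% / 29% / 30% | 30% |
| 0.3 per year, primary cut | 26% / 30% / 32% | 29% |

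The declining hazards are scaled to 30% by week 58 + 30 days. Mean time at risk at the final cut is 1.3 / 1.8 / 2.0 years on D+T against 1.2 on chemotherapy.

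**5. Sensitivity of the chemotherapy figure (0.3 per year, final).** If 20% stop chemotherapy early it is 27%, and the differences are +3 / +11 / +14 points. With eight weeks of delay it is 33%, and they are −3 / +5 / +8.

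**6. Scale against noise.** With 68 and 34 patients, the standard error of 38% versus 30% is √(0.381 × 0.619/68 + 0.301 × 0.699/34) = 0.098. A shift of 8 to 11 points is about one standard error.

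**7. Does a common-time measure remove it?** Under equal hazards, cumulative incidence is the same in both arms at any time inside both windows. At 0.3 per year it is 1 − exp(−0.3 × 0.613) = 16.8% at week 32 and 1 − exp(−0.3 × 1.073) = 27.5% at week 56. With 26-week halving it is 22.3% and 28.9%. Simulated Kaplan-Meier estimates, censored at the end of the on-treatment window, agreed between arms to within 0.001 at every D+T median. The first-event rate per patient-year is equal under a constant hazard (0.300 in each arm). Under 26-week halving at a 104-week median it gives 0.20 on D+T against 0.31 on chemotherapy despite equal hazards, which falsely favours D+T.

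**The case against.** The strongest reply is that nothing here is wrong. Incidence over each regimen as it is meant to be given is what a family faces, and preferring a per-time measure is a choice of question. Section 10.5.1.2 does not say that incidence is the only measure, and supplementary tables are ordinary SAP content. Exposure is reported for both arms, all events are listed, and no test or stopping rule uses these tables. The events of special interest are specific to D+T, so absolute incidence on D+T matters most, and no document supports equal hazards. The longer D+T medians come from previously treated patients, one of them from only 12.

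Much of this stands. Incidence is a valid burden summary, the size rests on assumed durations, and it can vanish or reverse. What remains is that the protocol defers several items to the SAP by name (censoring rules, notable safety values, crossover analyses) but states the adverse event measure itself. Applied to a by-arm comparison of a fixed course with open-ended treatment, that measure mixes hazard with time at risk. Reporting exposure separately lets a reader suspect this but not resolve it.

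A reader might go further and infer that the tables are invalid, that they will make D+T look less safe, or that no adjusted summary exists. The documents support none of these: the effect depends on event timing and D+T duration, and the SAP is not at hand. A reader might also infer that crossover patients' D+T events will be counted under chemotherapy. Section 10.5.1.1 does not say whether the window closes at crossover, but Table 7-2 treats crossover as its own period and 10.4.4, in the efficacy section, leaves crossover analyses to the SAP. That calls for clarification only.

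**Conclusion.** The point holds in a limited form. It concerns the final analysis and events that keep accruing. At an equal constant hazard of 0.3 per year with chemotherapy on schedule, the D+T excess is 0 to 11 points depending on D+T duration; allowing for early stopping or delay of chemotherapy widens the range to −3 to +14. It is at most a few points at the primary cut, absent for early-onset events and for hazards halving every 26 weeks, and about nil if D+T stops at a median near 52 weeks. The figures assume exponential stopping unrelated to event risk, uniform accrual at the 2019 rate, and a chemotherapy window that does not extend into crossover.

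The harm is to interpretation of the final safety comparison. Response rate, progression-free survival and overall survival are untouched. A worthwhile improvement, not a serious defect.

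**What to change.** Keep the incidence tables as the summary of treatment burden. In 10.5.1.2 add, for LGG events of special interest, serious events and grade 3 or higher events, the cumulative incidence of first event by arm at weeks 32 and 56, estimated by a Kaplan-Meier type method and censored at the end of the on-treatment window or the data cut. Both times lie inside the scheduled chemotherapy window. First-event rates per patient-year with 95% confidence intervals can be added as a secondary, descriptive measure, with the constant-hazard assumption stated, and read after the cumulative incidence.

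As a clarification in 10.5.1.1, say that the chemotherapy-arm window ends at the earlier of last chemotherapy dose + 30 days and first crossover D+T dose, with crossover-period events tabulated separately.

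The cost is a few tables from dates already collected. The cumulative incidence assumes that stopping treatment is unrelated to event risk. It gives no randomised comparison of events arising after the chemotherapy window, so the late events that prompt the concern should be described for D+T alone.
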